7.9.2.4 Determination of Patients/Data for Analysis

The Enrolled Population and, at each FU visit, the subset of subjects part of the Enrolled Population that were referred for sudden cardiac death risk (SCD) stratification and management will be included in the analysis.

7.9.3 Secondary objective 2: Proportion of post-acute patients who received an ICD/CRT-D

Characterize the proportion of post-acute MI patients who receive an ICD/CRT-D within 12 months post-MI.

7.9.3.1 Hypothesis

There are no hypotheses for this objective, as this is a characterization objective.

7.9.3.2 Endpoint definitions

The endpoint will be defined as whether a subject received an ICD/CRT-D device during follow-up.

7.9.3.3 Analysis methods

At each follow-up visit (3 months, 6 months, 12 months), the proportion of subjects who received an ICD/CRT-D will be computed.

The numerator will be the number of subjects who were implanted at a given follow up visit. In the Implant CRF, these subjects will have answer “yes” to the question “Has the subject received an ICD or CRT-D?”.

The denominator will be either the Enrolled Population or a composite of the below:

- (a) ***all patients meeting an indication for implant and not having been implanted at the previous visits.*** That is, within the Implant CRF form, all subject that at any previous visits will have answer “yes” to the question “did the subject meet an indication for an ICD or CRT-D?”, and at all previous visits will have answer “no” to the question “has the subject received an ICD or CRT-D?”
- (b) ***all patients meeting an indication for implant at the given visit.*** That is, within the referral CRF form, all subject that at a given visit will have answer “yes” to the question “did the subject meet an indication for an ICD or CRT-D?”

A SAS code similar to the example SAS code shown in Section 7.9.1.3 will be used. Separately for each follow up visit, the results will be shown in a table similar to Table 6 below, where “Indicated for an ICD/CRT-D” is the denominator above.

Table 6: Proportion (95% CI) of subjects who receive ICD/CRT-D at visit X

	Enrolled Population		Indicated for an ICD/CRT-D Population	
Region	n/N (%)	95% CI	n/N (%)	95% CI
Region 1	XX/XX (XX.XX%)	(XX.XX% - XX.XX%)	XX/XX (XX.XX%)	(XX.XX% - XX.XX%)
Region 2	XX/XX (XX.XX%)	(XX.XX% - XX.XX%)	XX/XX (XX.XX%)	(XX.XX% - XX.XX%)
...
Overall	XX/XX (XX.XX%)	(XX.XX% - XX.XX%)	XX/XX (XX.XX%)	(XX.XX% - XX.XX%)

In addition to the above analyses, logistic regression models similar to the example model in Section 7.9.1.3 might be fitted overall and by region, to estimate the odds ratios of being implanted, depending on different factors, such as age, gender, specialty of physician who implanted, type of device received – ICD or CRT-D, PCI versus non-PCI, STEMI versus non-STEMI. Results will be displayed either by means of either tables or of plots.

Additional analysis:

A competing risk event curve with accompanying 95% confidence bounds and mortality accounted for, will be produced for each region, to assess a subject's time from enrollment to:

- (a) Having met the referral criteria;
- (b) Having been referred;
- (c) Having had an SCD stratification visit;
- (d) Having been indicated an ICD/CRT-D implant
- (e) Having received an ICD/CRT-D.

An SAS code for the competing risk analysis similar to the below will be used:

```
proc lifetest data=KM plots=cif(test) timelist=0 1 2 3 4 5 6 7 8 9 10 11 12;
  by region;
  time T*Status(0) /eventcode=1;
  strata Event / order=internal;
run;
```

where Event is a categorical variable with categories the event of interest (meeting the referral criteria, having been referred, having had an SCD risk stratification visit, having been indicated for an ICD/SCD-D implanted, having received an ICD/CRT-D), T is the time in months from enrollment to the date of the event of interest and Status is an indicator variable with 3 values: 0 for censored observations, 1 observations related to the event of interest and 2 observations related to subjects who died. Note that the dataset to be used will contain one row for each event per subject (e.g.: if a subject will have all events, from having met the referral criteria to having received the ICD/CRT-D, the dataset will contain 5 rows for that subject).

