9.3. Schedule of Events

Clinical data will be collected at the Baseline 3 month, 6 month, 12 month, and exit visits. In addition if applicable, clinical data will be collected with an exit or death, as well as unscheduled visits. Device data will be collected from device interrogations on Medtronic devices received during the period between the enrollment and exit until study closure; for non-Medtronic devices, device data will not be collected. Data will be collected using eCRFs using an electronic data management system for clinical studies. In addition to eCRF data, non-eCRF data will be collected including device interrogation files (for Medtronic implanted devices only). Surveys may also be used throughout the study.

Data will be stored in a secure, password-protected database, which will be backed up nightly. Data will be reviewed using programmed and manual data checks. Data queries will be made available to study sites for resolution. Study management reports will be generated by Medtronic to monitor data quality and study progress. At the end of the study, the data will be frozen and retained indefinitely by Medtronic. Data Collection requirements are summarized in the table 2 below.

Table 2 Data Collection and study procedure requirements at subject visit

Study Procedure	Baseline	3 month visit	6 month visit	12 month visit	Study Exit
Patient informed consent	X				
Eligibility Verification (Inclusion/ exclusion assessment)	X				
Subject Demographics	X				
Acute MI information	X				
Medical History	X				
Cardiovascular Medications	X	X			
LVEF measurement	X	X*	X (collect if performed as per SOC)	X (collect if performed as per SOC)	
ECG	X	X (collect if performed as per SOC)	X (collect if performed as per SOC)	X (collect if performed as per SOC)	
Referral Status		X	X	X	X
Implant Status (if applicable)		X (if subject receives or has received device implant)	X (if subject receives or has received device implant)	X (if subject receives or has received device implant)	X (if subject receives or has received device implant)
Device Interrogation File (pdd) or CareLink Transmission for subjects implanted with Medtronic device only		X	X	X	X
Adverse Event	As they occur				
System Modification					
Study Deviation					
Subject Death					

* The LVEF measurement needs to be performed ≥ 40 days post-acute MI for MI subjects without revascularization, or ≥ 90 days post-revascularization for post-MI subjects with revascularization done.

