7.9.1.4 Determination of Patients/Data for Analysis

The Enrolled Population will be included in the descriptive statistics shown in Table 1.

At each FU visit, the subset of subjects of the Enrolled Population that at that visit will have a reason for referral will be used to compute the descriptive statistics shown in Table 2 and the odds ratios of referral.

7.9.2 Secondary objective 1: Proportion of post-acute MI patients who are indicated for an ICD/CRT-D

Characterize the proportion of post-acute MI patients who are known to be indicated for an ICD/CRT-D within 12 months post-MI

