7.9.2.2 Endpoint definitions

The endpoint will be defined as whether a subject was indicated for an ICD/CRT-D device during follow-up.

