It may also happen that a patient might have an SCD risk stratification visit without having been referred, for example, patients who had an SCD risk stratification visit for secondary prevention. An additional table will then be created to show, for each visit, the number of subjects that were not referred but had an SCD risk stratification visit and among those, the proportion of subjects that had a reason for referral.

Second, the proportion and Wilson score 95% CI of subjects recommended for ICD/CRT-D at the three months visit, at the 6 months and at the 12 months visits will be computed overall and by region, for the Enrolled Population and for the subjects in the numerator in table 3 above, that is, all subjects that have had an SCD risk stratification visit (called in table 4 below “SCD risk stratification Population””).

A SAS code similar to the example SAS code shown in Section 7.9.1.3 will be used. For each follow up visit, the results will be shown in a table similar to Table 5 below.

Table 5: Proportion (95% CI) of subjects indicated to receive ICD/CRT-D, at visit X

Region	Enrolled Population		SCD risk stratification population	
	n/N (%)	95% CI	n/N (%)	95% CI
Region 1	XX/XX (XX.XX%)	(XX.XX% - XX.XX%)	XX/XX (XX.XX%)	(XX.XX% - XX.XX%)
...
Overall	XX/XX (XX.XX%)	(XX.XX% - XX.XX%)	XX/XX (XX.XX%)	(XX.XX% - XX.XX%)

Where n is number of the subjects “recommended for ICD/CRT-D” and N is either the Enrolled Population or the SCD risk stratification population.

In addition to the above analyses, logistic regression models similar to the example model in Section 7.9.1.3 might be fitted overall and by region, to estimate the odds ratios of being indicated for an ICD/CRT-D, depending on different factors, such as sex, age, specialty of physician who performed the ICD/CRT-D risk stratification, type of device received – ICD or CRT-D, PCI versus non-PCI patients, STEMI versus non-STEMI patients . Results will be displayed either by means of either tables or of plots.

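### Secondary objectives 1 and 2 ask for 12-month proportions, but SAP Tables 5 and 6 are per visit, and the only cumulative estimate censors subjects who exit with LVEF ≥50%, probably informatively

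*SAP*

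**What the plan says.** Objective 1 (SAP 7.9.2) is to "Characterize the proportion of post-acute MI patients who are known to be indicated for an ICD/CRT-D within 12 months post-MI". Objective 2 (SAP 7.9.3) is to "Characterize the proportion of post-acute MI patients who receive an ICD/CRT-D within 12 months post-MI". Both endpoints are ever/never: "The endpoint will be defined as whether a subject was indicated for an ICD/CRT-D device during follow-up" (SAP 7.9.2.2) and "The endpoint will be defined as whether a subject received an ICD/CRT-D device during follow-up" (SAP 7.9.3.2).

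The tables are laid out one per visit.

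- **Table 5** (SAP 7.9.2.3): the proportion of "subjects recommended for ICD/CRT-D at the three months visit, at the 6 months and at the 12 months visits will be computed". The count n is not defined as new or cumulative.
- **Table 6** (SAP 7.9.3.3): "The numerator will be the number of subjects who were implanted at a given follow up visit". The denominator is either the Enrolled Population or a composite. Limb (a) of the composite is "all patients meeting an indication for implant and not having been implanted at the previous visits". Limb (b), subjects indicated at the given visit, has no such restriction.

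SAP 7.9.3.3 then plans, as an additional analysis, competing-risk curves by region from enrollment to five milestones, including indication and implant, read monthly to month 12. Status has three values: censored, event of interest, died. Protocol 12.3.1.3 and 12.3.2.3 call for these curves too.

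Subjects with LVEF ≥50% at 3 months leave the study even if they have another reason for referral (SAP 7.9.1.3), and nothing is collected afterwards (Protocol 9.7). Protocol 12.5 censors survival endpoints at exit.

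**The concern.** There are two gaps between the question and the planned answer.

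First, an ever/never endpoint over 12 months needs a cumulative count. If Table 6 counts new implants, its 12-month Enrolled column shows only those added since the 6-month visit, and a reader could take that for the 12-month implant rate. The text is also mixed. The CRF item that selects the numerator asks whether the subject has received a device, which is a status, and Protocol Table 2 (section 9.3) collects implant status "if subject receives or has received device implant". A programmer could defend either count.

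Second, the one estimate that is cumulative rests on an assumption that neither document states or varies: that subjects removed because their LVEF recovered have the same later chance of indication or implant as those who remained. Since LVEF of 40% or less is a listed reason for referral, a lower chance is more plausible, and the curve would then be too high after month 3.

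**Working it through.** **Figures in the plan.** The documents give no expected indication rate, implant rate or share with LVEF ≥50%, so there is no planned figure to reproduce for these objectives. The regional size used below does reproduce: 54/0.30 = 180 and 180/0.90 = 200 (SAP 6.1).

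**New or cumulative?** Three things point to new counts in Table 6: the numerator wording, limb (a), and SAP 7.9.2.3, whose worked example for Table 4 counts at 6 months only those seen at that visit. Two things do not exclude earlier implants: the CRF item and limb (b). Table 5 has no rule for n.

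Illustration, with assumed counts: 200 enrolled, 16 implants over the year, between 2 and 8 of them after the 6-month visit. Wilson 95% limits are (p + z²/2n ± z√[p(1−p)/n + z²/4n²])/(1 + z²/n).

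- New counts, 12-month Enrolled cell: 2/200 = 1.0% (0.3–3.6%) up to 8/200 = 4.0% (2.0–7.7%).
- Ever implanted: 16/200 = 8.0% (5.0–12.6%).

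**How exits enter the curve.** With only three Status values, a living, event-free subject who exits can only be coded 0. Protocol 12.5 agrees.

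**Effect of that censoring.** Let p be the later event chance of those who stay, q the share of those at risk who exit at 3 months, and r the exited subjects' later chance relative to p.

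- True post-3-month part: p(1−q) + q·r·p = p(1−q+qr)
- Exits censored: the curve estimates p, so the ratio to truth is 1/(1−q+qr)
- Exits as a competing event: the curve estimates p(1−q), so the ratio is (1−q)/(1−q+qr)

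| r | Censored, q = 20% / 30% / 40% | Competing event, q = 20% / 30% / 40% |
|---|---|---|
| 0 | 1.25 / 1.43 / 1.67 | 1.00 / 1.00 / 1.00 |
| 0.5 | 1.11 / 1.18 / 1.25 | 0.89 / 0.82 / 0.75 |
| 1 | 1.00 / 1.00 / 1.00 | 0.80 / 0.70 / 0.60 |

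For 0 ≤ r ≤ 1 the first ratio is never below 1 and the second never above it, so the two versions bracket the truth.

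**The same on the whole curve** (assumed: 10 deaths and 10 drop-outs before 3 months, matching the plan's combined 10%; a = 8 implants by 3 months, b = 8 later; x of the 180 exit). With exits censored, F = 0.95·[a/180 + ((180−a)/180)·b/(180−a−x)].

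- x = 36: 0.95·[8/180 + (172/180)·(8/136)] = 9.6%
- x = 54: 10.4%
- x = 72: 11.5%
- Exits as a competing event, any x: 0.95·16/180 = 8.4%
- Truth if r = 0.5: 9.0%, 9.4%, 10.0%, each between the two versions

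With the implants split 12+4 the censored curve runs 9.0–10.0%; with 4+12 it runs 10.1–12.8%.

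**Time origin.** The curve starts at enrollment, up to 30 days after the MI, so its month 12 can fall as late as day 365 + 30 = 395 post-MI. The 12-month visit window also closes at day 395, and later visits are still analysed (SAP 5.1).

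**The case against.** The case on the other side is substantial.

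- **A 12-month estimate is planned.** The curve covers both indication and implant to month 12 with 95% bounds. That stands: a reader might infer that the SAP has no cumulative answer at all, and the documents do not support this.
- **The exit coding is settled.** A reader might infer that it was left open. Status and Protocol 12.5 leave only censoring. What remains is whether that censoring is informative.
- **Table 6 leans clearly to new counts, and nothing is lost.** The Enrolled denominator is fixed, so the three visit counts can be added to give the crude proportion. This is right on the new-count reading; on the status reading the sum would double-count. Visit counts also follow visit timing and not the 12-month limit.
- **These are secondary, descriptive objectives without hypotheses, and the tables are example shells.** This limits the importance but does not remove the mismatch.
- **Exited subjects may still be implanted later.** SAP 7.9.1.3 itself expects some to have non-LVEF reasons for referral, so r need not be 0. That is why neither version of the curve should stand alone.

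**Conclusion.** The point holds as a worthwhile, inexpensive improvement. On its natural reading, Table 6 gives increments where objective 2 asks for a 12-month proportion; Table 5 leaves the same question undefined for objective 1. The cumulative curve that fills the gap is probably biased upward after month 3, because it treats recovered, exited subjects like those who stayed. No sensitivity analysis is planned, and no data after exit can test the assumption.

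The size is unknown. The factor of 1.25–1.67 is the extreme case of no later implants among exited subjects, for an assumed 20–40% exiting; it falls to 1.11–1.25 at r = 0.5 and disappears at r = 1. It applies only to the post-3-month part of the curve. It should not be read as an expected bias: q, r and all implant counts above are assumptions.

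**What to change.** 1. In SAP 7.9.2.3 and 7.9.3.3, label the per-visit counts in Tables 5 and 6 as new since the previous visit. Add one cumulative row to each: ever indicated, or ever implanted, within 12 months post-MI by event date, over the Enrolled Population, with Wilson 95% CI, by region and overall. Footnote that exits and drop-outs count as non-events.
2. Keep the protocol's curve with exits censored, and say so. Report it a second time with LVEF ≥50% exits as their own competing event. State that for 0 ≤ r ≤ 1 the two versions bracket the truth and that neither verifies the assumption. Note that time runs from enrollment and not from the MI.

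The cost is some SAP wording, one row per table and one repeat run, with no new data: the curve already needs the event dates. The trade-off is that the crude row may be low, because exits and drop-outs count as non-events, and the competing-event version may be low, because it allows exited subjects no later indication or implant.

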7.9.2.3 Analysis methods

Among all subjects referred, the proportion of subjects that had an SCD risk stratification visit will firstly be computed, followed by the proportion of subjects that were indicated for ICD/CRT-D implant. Details of the computations are described below.

First, at each follow-up visit, among all patients who were referred for SCD risk stratification, the proportion of those who had an SCD risk stratification visit will be computed.

For any given follow-up visit (3 months, 6 months, 12 months), the denominator will be patients referred for SCD risk stratification up to the given visit and the numerator will be all patients that, among the patients included in the denominator, will have an SCD risk stratification visit

In the referral CRF, the patients included in the denominator will be a composite of the below:

- (a) ***all patients that were referred but did not have any ICD risk stratification visit at any previous follow-up visit.*** That is, within the referral CRF form, all subject that at any of the previous visits will have answer “yes” to the question “has the subject been referred or invited for SCD risk stratification?” and answer “no” to the question “was the SCD visit performed?”.
- (b) ***all patients being referred at the given visit.*** That is, within the referral CRF form, all subject that at a given visits will have answer “yes” to the question “has the subject been referred or invited for SCD risk stratification?”.

The subjects included in the numerator will be all subjects part of the denominator that will have answer “yes” to the question “was the SCD visit performed?”.

For example, at the 6 months visit, the numerator will be all patients that had their SCD risk stratification visit at the 6 months visit and the denominator will be all patients who were referred but did not have their SCD risk stratification visit within the 3 months visit window and of all patients that were referred at the 6 months visit.

The results will be shown in a table similar to table 4 below:

Table 4: Number (%) of subject that had their SCD risk stratification visit

	3 months visit	6 months visit	12 months visit
Region 1	XX/XX (XX.XX%)	XX/XX (XX.XX%)	XX/XX (XX.XX%)
Region 2	XX/XX (XX.XX%)	XX/XX (XX.XX%)	XX/XX (XX.XX%)
...
Overall	XX/XX (XX.XX%)	XX/XX (XX.XX%)	XX/XX (XX.XX%)

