7.9.3.4 Determination of Patients/Data for Analysis

The Enrolled Population and, at each FU visit, the subset of subjects that were indicated for an ICD/CRT-D will be included in the analysis as described in Section 7.9.3.3.

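### Denominator limb (a) of SAP Table 6 (indicated column) and Table 4 keeps subjects in N after they have died or left the study

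*SAP*

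**What the plan says.** SAP 7.9.3.3 tabulates device receipt separately at 3, 6 and 12 months. On the numerator it says: "The numerator will be the number of subjects who were implanted at a given follow up visit". These subjects are found through an Implant CRF question on whether a device has been received. On the denominator: "The denominator will be either the Enrolled Population or a composite of the below". The composite has two limbs:

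- Limb (a): "all patients meeting an indication for implant and not having been implanted at the previous visits". Its CRF rule is "That is, within the Implant CRF form, all subject that at any previous visits will have answer" yes to the indication question, together with no to device received at all previous visits.
- Limb (b): "all patients meeting an indication for implant at the given visit".

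SAP 7.9.3.4 adds only that "at each FU visit, the subset of subjects that were indicated for an ICD/CRT-D will be included in the analysis".

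Table 4 (SAP 7.9.2.3) is built the same way for risk-stratification visits. Its limb (a) is "all patients that were referred but did not have any ICD risk stratification visit at any previous follow-up visit", and its CRF rule asks for a referral and a visit not performed at any one of the previous visits.

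Two other provisions matter. Protocol 9.7 states that no study data are collected after exit. SAP 7.4 states that the main analysis of each objective does not account for missing data.

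**The concern.** Neither limb (a) says that a carried-forward subject must still be in the study. Someone indicated at 3 months who dies or exits before 6 months cannot be recorded as implanted between 6 and 12 months, yet can be counted in the 12-month N. The same goes for a referred subject who left before being seen.

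The study exists to describe treatment patterns by geography (Protocol 12.1), and SAP 6.2 expects death and drop-out to differ between geographies. If the denominator absorbs past attrition, a region that loses more subjects looks like a region that treats fewer of its indicated patients. Only the indicated column of Table 6 is exposed to this; limb (a) plays no part in the Enrolled Population column.

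**Working it through.** **The plan's own figures.** No value is stated for Table 6. The sample-size figures in SAP 6.1 do reproduce: 54 is the first n with at least 80% probability of a Wilson 95% half-width of 0.125 or less at 70% (0.897, against 0.784 at n = 53); 54/0.30 = 180; 180/0.90 = 200.

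**Who stays in N at 12 months.** Take a subject positive at 3 months (indicated and not implanted, or referred and not seen) who dies or exits before 6 months.

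- Table 4: the 3-month answers alone meet a rule that looks at any previous visit, so the subject is in the 12-month N.
- Table 6: the rule needs no device at all previous visits, and this subject has no 6-month form. If a missing form does not count against the rule, the subject stays (reading A). If it does, the subject drops out (reading B), but so does a living subject who merely missed the 6-month visit. The SAP does not choose.

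At 6 months, anyone who completed the 3-month visit and remained in the study was at risk when the interval began, so limb (a) is sound there.

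**Size for Table 6.** The documents give no indication, implant or post-3-month loss rates. Assume:

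- about 38 indicated at 3 months per region (54 × 0.70 = 37.8, an upper figure that treats every referred subject as indicated)
- a share l lost to death or exit in each interval
- a share q implanted, at 3 months among all 38 and afterwards among those still in the study at the end of each interval
- no new indications.

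R is the number unimplanted after 3 months; the starting count cancels in the proportions.

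- New implants by 6 months: qR(1−l)
- 12-month N, reading A: R − qR(1−l)
- 12-month N, subjects in the study at the start of the interval: R(1−l)(1−q)
- New implants by 12 months: qR(1−l)²(1−q)

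For q = 0.30 and l = 0.10: R = 38 × 0.70 = 26.6; 6-month implants 0.30 × 23.94 = 7.18; N under reading A 26.6 − 7.18 = 19.42; N in the study at the start 23.94 − 7.18 = 16.76; 12-month implants 0.30 × 16.76 × 0.90 = 4.52. The proportions are 4.52/19.42 = 23.3% and 4.52/16.76 = 27.0%.

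| q | l | 12 months, reading A | 12 months, in study at start | Shortfall (points) |
|---|---|---|---|---|
| 30% | 5% | 26.5% | 28.5% | 2.0 |
| 30% | 10% | 23.3% | 27.0% | 3.7 |
| 30% | 20% | 17.7% | 24.0% | 6.3 |
| 10% | 5% | 9.0% | 9.5% | 0.5 |
| 10% | 10% | 8.0% | 9.0% | 1.0 |
| 10% | 20% | 6.3% | 8.0% | 1.7 |

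Under these assumptions reading B gives the same result as the fourth column.

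**Regional comparison.** Two regions with the same q = 30% but losses of 5% and 20% differ by 26.5 − 17.7 = 8.8 points under reading A, and by 28.5 − 24.0 = 4.5 points with the start-of-interval set. The remaining 4.5 points come from losses within the interval.

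**The opposite direction.** The numerator question is cumulative, and Protocol Table 2 collects implant status from subjects who receive or have already received a device. Limb (b) does not exclude those already implanted. For q = 0.30 and l = 0.10 at 6 months, counting new implants only gives 7.18/26.6 = 27.0%. Counting everyone who has ever received a device and is still in the study adds 11.4 × 0.90 = 10.26, giving 17.44. That is 17.44/26.6 = 65.6% on limb (a) alone, or 17.44/(26.6 + 10.26) = 47.3% if implanted subjects re-enter through limb (b).

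**The case against.** The strongest reply is that the SAP never states which proportion it wants, and that keeping subjects who die is legitimate if the target is uptake among those known to be indicated. This stands for deaths and exits within the interval: those subjects were at risk for part of it, and implant status is also collected at study exit. It does not cover subjects gone before the interval began, in a table that removes implanted subjects as it goes along. That set is neither a cumulative nor an at-risk denominator.

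It is also fair that the protocol's analysis (12.3.2) uses all enrolled subjects, that the Enrolled Population column supplies this, and that exits by reason, drop-outs between visits and cardiovascular deaths are reported elsewhere. Precision is limited too: for 4 implants among 20, the Wilson 95% interval runs from about 8% to 42%, so the illustrated shifts lie inside it. But they are systematic and follow regional attrition.

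Some stronger readings are not supported:

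- *Everyone ever indicated is carried forward.* No: limb (a) removes subjects implanted at an earlier visit.
- *The proportions are simply too low.* Only if new implants alone are counted; the cumulative question can reverse the direction.
- *Table and curve must conflict.* The SAP plans that "A competing risk event curve with accompanying 95% confidence bounds and mortality accounted for, will be produced for each region", but this runs from enrollment, and a competing-risk curve also keeps subjects who die as never implanted. A difference would not be an inconsistency.
- *Subjects who lose their indication inflate N.* Whether the question is answered afresh at each visit cannot be seen without the CRFs.

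**Conclusion.** The concern holds in a limited form. Limb (a) has no in-study condition in either table. Subjects who died or exited before 6 months certainly stay in the 12-month N of Table 4; in the indicated column of Table 6 they stay unless a missing 6-month form is read as failing the rule, which would also drop living subjects who missed that visit. With new implants only, the illustrated 12-month shortfall is 0.5 to 6.3 percentage points. It rests on assumed losses of 5% to 20% per interval, 10% or 30% implanted, no new indications and reading A; the documents cannot fix it. The numerator and limb (b) need settling in the same edit, since read literally they could outweigh the shortfall. The matter concerns secondary objectives and leaves the primary analysis untouched.

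**What to change.** In SAP 7.9.3.3:

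- Define N at each visit as subjects alive, in the study and not implanted at the start of the interval since the previous visit, with an indication recorded by then, plus subjects newly indicated in the interval and not already implanted. State how the start is set when the previous visit was missed.
- Limit the numerator to new implants in that interval within this set, including those reported at exit or before death.
- Keep subjects who die or exit during the interval in N. Show their number, and the number whose latest indication answer is no, as separate counts under the table.

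In SAP 7.9.2.3, restrict Table 4 limb (a) to subjects in the study and not yet seen at the start of the interval.

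Do not restrict limb (a) to subjects who completed the visit. That conditions on surviving the interval and would lose a subject implanted in it who then died.

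The cost is SAP wording and one filter per table. The time-to-event analyses already planned need the same event, death and exit dates, so no new data are required. Denominators at 12 months become somewhat smaller.
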